3.2.3 Interventions

The control group will receive isoflurane for maintenance of anaesthesia. The intervention group will receive desflurane for maintenance of anaesthesia.

Standard protocols for induction and maintenance of anaesthesia will be followed, as discussed with Prof. [name], an international expert in the field of desflurane use. A detailed leaflet describing the protocol has been developed (see Appendix 6.5), which will be handed to the treating anaesthetist on the day of surgery.

- Confirm anaesthetic workstation has passed the machine check, and record any machine leak, if present.
- Intravenous Induction of Anaesthesia:
 - Fentanyl 1.5-3 mcg/kg pre-induction to reduce airway responses during manipulation. Lower doses to be used for short procedures and larger dose for longer procedures.
 - Lignocaine 40 mg pre-induction to minimize Propofol-induced injection pain.

- Propofol 2-2.5 mg/kg until induction of anaesthesia.
- Dexamethasone 8mg after induction of anaesthesia to prevent post-operative nausea and vomiting and to decrease opioid requirements.
- Mask ventilation with 6 l/min 100% oxygen until airway is placed.
- Airway management will be with a Laryngeal Mask Airway (LMA), size selected according to patient weight.

- Use of Muscle Relaxants During Procedure:
 - If required, a small dose of muscle relaxant may be administered to facilitate immobility during the procedure.
 - For Rocuronium, a dose of up to 0.15mg/kg may be used (about 10-15mg for most adults). This dose is a quarter of the normal intubating dose for Rocuronium.
 - For Cisatracurium, a dose of up to 0.05mg/kg may be used (about 2.5 – 4mg for most adults). This dose is a quarter of the normal intubating dose for Cisatracurium.
 - Top-up doses may be given every 30-40 minutes, if required; dosing should be the same as the initial dose.
- Maintenance of Anaesthesia:
 - Isoflurane:
 - After the airway is secured, fresh gas flow is reduced to 2 l/min and the Isoflurane vaporiser is opened and adjusted to attain 1MAC.
 - Once 1MAC is attained, the fresh gas flow will be reduced to 0.2-0.5 l/min and the vaporiser will be adjusted to maintain 1MAC. The aim will be to reduce the fresh gas flow as low as possible, taking into consideration the amount of machine and/or circuit leak.
 - If basal flow (0.2L/min) is reached, FiO₂ will be set to 100% to meet the patient's oxygen demand.
 - Should the bag on the anaesthetic machine collapse during minimal or basal flow anaesthesia (e.g. because of a poor seal from the LMA, or due to circuit leak) the following steps should be taken: increase the fresh gas flow to 2 L/min and adjust the vaporiser concentration to maintain 1MAC, allow the bellows to fill and then return to the previous concentration and fresh gas flow settings.
 - Desflurane:

- After the airway is secured, fresh gas flow is reduced to 2 l/min and the desflurane vaporiser is opened to 12%. This is maintained until 1MAC is reached, usually about 3-5 minutes.
- The fresh gas flow will then be turned down to 0.2-0.5 l/min and the vaporiser adjusted to maintain 1MAC. The aim will be to reduce the fresh gas flow as low as possible, taking into consideration the amount of machine and/or circuit leak.
- If basal flow (0.2L/min) is reached, FiO₂ will be set to 100% to meet the patient's oxygen demand.
- Should the bag on the anaesthetic machine collapse during minimal or basal flow anaesthesia (e.g. because of a poor seal from the LMA, or due to circuit leak) the following steps should be taken: turn the vaporiser concentration to 12% and the fresh gas flow to 2 L/min, allow the bellows to fill and then return to the previous concentration and fresh gas flow settings.
- The use of minimal or basal fresh gas flow is intentional, to minimise the amount of anaesthetic vapour used. When basal flow is used, 100% oxygen is required to meet patient's oxygen demand.
- Managing Potential Problems:
 - Should the ophthalmologist complain that the patient is in too light a plane of anaesthesia, the patient may be deepened with a bolus of Propofol 0.5-1 mg/kg.
 - For intra-operative analgesia (for example if patient develops tachycardia or hypertension), administer 50mcg Fentanyl boluses intravenously.
 - When post-operative analgesia is required, administer 50-100mg of Tramadol intravenously as a bolus 20 minutes before the end of the procedure.
 - For post-operative nausea or vomiting (only if required), administer 4mg of Ondansetron intravenously as a bolus, followed by 10mg of Metoclopramide after 30 minutes (only if further treatment is required).
- End of Procedure:
 - If a small dose of muscle relaxant was used, the effects should be reversed with Neostigmine 0.04mg/kg (2-3mg for most adults) 10-20 minutes before the end of the procedure. Glycopyrrolate or Atropine may be added to prevent bradycardia and gastro-intestinal side-effects.
 - The vaporisers will be closed, and fresh gas flow will be increased to 6 l/min in order to wash out the volatile anaesthetic.
- Recovery and Discharge

- The patient will be taken to the recovery room when they are able to protect their airway, as per normal practice.
- Discharge from the recovery room to the ward will be according to the standard procedures in the post-anaesthesia recovery room. Patients should score at least 9 on the modified Aldrete score, with the patient awake and alert with stable vital signs, not experiencing any acute side effects (e.g., nausea or vomiting) or moderate-to-severe pain.

3.2.4 Materials, Apparatus and Instruments

Basic Materials and Apparatus:

- Patients will be induced in the ophthalmology theatre; anaesthesia will be maintained with the Datex-Ohmeda Aisys CS2 anaesthetic workstation.
- Isoflurane is freely available, and the standard anaesthetic vapour that is used in our setting.
- Desflurane will be purchased for use in the study.
- Vaporisers for both isoflurane and desflurane are available in our theatre complex.
- Nitrous Oxide will not be used as part of the fresh gas mixture, because it is not always available in our setting.
- Standard monitors will be used during anaesthesia: non-invasive blood pressure monitoring, pulse oximetry, 3-lead electrocardiogram, capnography and gas analysis.

Instruments:

Quality of Recovery will be measured with the 15-Item Quality of Recovery score (QoR-15):

- The English version can be used for English-speaking patients. There is no copyright on the form (confirmed by the author, Prof. [name] via email).
- The form will be translated into Afrikaans and Setswana.
 - Forward translation has been done in advance by an accredited medical translator at Zwelinhle Translation Services.
 - Back translation of both translations has been done by a separate panel of health care professionals, who were blinded to the original English version. Three Setswana home language speakers did the back-translation for the Setswana version, and three Afrikaans home language speakers did the back-translation for the Afrikaans version.
 - The final versions have been corrected and adapted by all panel members.
 - See Appendices 6.9 and 6.10 for the translated versions.

- The QoR-15 is a validated and reliable tool for measuring quality of recovery. The patient is asked to rate their experience of 15 items from 0 (worst score) to 10 (best score).
- Where possible, the QoR-15 form will be handed to the patient to complete by themselves. However, in cases where patients are visually impaired, the items on the questionnaire will be read to them, and their responses recorded.

3.2.5 Feasibility

Consensus on the **acceptability feasibility** of the treatment protocol has been obtained from peers and colleagues in the Department of Anaesthesia by circulating the proposed standardised treatment protocol (see Appendix 6.5) and asking for feedback.

Eleven feasibility questionnaires were completed (See Appendix 6.2 for template of the questionnaire). All 11 respondents indicated that they thought the protocol to be practical and easy to follow. All 11 respondents indicated that they would be comfortable giving anaesthesia according to the treatment protocol. Five respondents have never used Desflurane before in clinical practice; of these 3 respondents were subsequently taught how to use Desflurane during a training workshop, the other 2 respondents were instructed on the use of Desflurane by the Chief Researcher during clinical cases.

Most of the concerns recorded on the forms related to the use of basal fresh gas flow. One respondent commented that the technique is labour-intensive and user-dependent. The same respondent was concerned about flushing the circuit with oxygen only when the bellows collapse, as this may lead to a drop in MAC, which may cause the patient to be in too light a plane of anaesthesia. One respondent was concerned about using basal flow with a Laryngeal Mask Airway, as there may be a leak if the airway does not seal properly. Another respondent was concerned about using basal fresh gas flow with the Drager Perseus anaesthetic workstation, as the bag tends to collapse when fresh gas flows below 0.6 l/min are used. One consultant anaesthetist was concerned about potential for carbon dioxide retention with basal flow anaesthesia and exhausted carbon dioxide absorber. These concerns are addressed in the changes to the treatment protocol – see below. One respondent was concerned about laryngospasm and bronchospasm – this is rarely a problem when Desflurane is used according to the recommended protocol with a maximum fresh gas flow of 2L and maximum vaporiser concentration of 12%.

- Treating anaesthetist to test the machine daily, as per standard practice, with a clean circuit. Carbon dioxide absorber should be checked daily and replaced when needed. The treating anaesthetist will record the machine leak as determined during the machine check.
- Allow fresh gas flow of 0.2-0.5 l/min, aiming to reduce the fresh gas flow as low as possible, taking into consideration the machine leak. This change allows the treating anaesthetist to adjust the fresh gas flow according to the amount of leak in the circuit. All responding anaesthetists felt more comfortable with this adjustment to the protocol.
- Steps to take when the bellows collapse: increase the fresh gas flow to 2 l/min and increase the concentration on the vaporiser to maintain 1MAC (maximum 12% for Desflurane). This will prevent a decrease in the MAC from flushing the circuit with oxygen only.
- In some cases, a small dose of muscle relaxant may be used to facilitate immobility during the procedure. The dose of muscle relaxant will be limited to 25% of the intubating dose, and reversal with neostigmine (plus glycopyrrolate or atropine) is mandatory. Glycopyrrolate is preferred, but it is currently out of stock.

This small dose of muscle relaxant should not affect the patient's post-operative quality of recovery, especially if it is reversed.

- Dose of Fentanyl changed to 1.5-3mcg/kg, to allow for smaller doses to be given for short procedures lasting 30 minutes or less.
- In cases where post-operative pain is expected, the treating anaesthetist may administer 50-100mg Tramadol 20 minutes before the end of the procedure, rather than waiting until the patient was in the recovery room.
- The anaesthetic workstation in the ophthalmology theatre has been changed to a Datex-Ohmeda CS2, which gives a clear indication of the amount of circuit leak after the machine check, and experience has shown that it has a smaller baseline leak than the Drager Perseus workstation.

The changes made to the standardised anaesthesia treatment protocol makes it more practical and pragmatic, and it will improve adherence to the study protocol. This will prevent exclusion of cases which were not treated according to the study protocol.

3.2.6 Outcomes

Primary outcome measures:

- Quality of recovery will be assessed in all participants with the QoR-15 score.
 - A baseline QoR-15 will be measured pre-operatively, and a repeat measurement will be done on day 1 post-operatively before discharge.
 - For each patient, the pre- and post-operative QoR-15 scores will be recorded, as well as the difference between the two measurements. The mean and median differences between the pre- and post-operative QoR-15 scores of the control group and the intervention group will be compared and tested for significance.
 - The mean and median post-operative QoR-15 scores of the control group and the intervention group will be compared and tested for significance.

[figure not shown]
Secondary outcome measures:

- To evaluate the consumption and cost of isoflurane and desflurane with a minimal or basal anaesthetic technique:
 - The vapour use per case in millilitres will be recorded from the anaesthetic machine.
 - The purchase price for isoflurane and desflurane will be obtained from the pharmacy.
 - The mean and median consumption of vapour between the two groups will be compared.
 - The mean and median cost of isoflurane and desflurane will be compared.

- To evaluate time in recovery:
 - The time the patient enters and leaves the recovery room will be recorded, as well as the total time the patient spends in the recovery room.
 - The mean and median time spent in recovery will be compared between the two groups.

3.2.7 Participant Timeline and Flow-Diagram

	STUDY PERIOD			
	Enrolment	Allocation	Post-allocation	Close-out
TIMEPOINT:	Day -1	Day 0	Day 0	Day 1
ENROLMENT				
Eligibility screen:	X			
Informed consent:	X			
Data Collection Form Section A:	X			
ALLOCATION		X		
INTERVENTIONS				
Isoflurane protocol:			X	
Desflurane protocol:			X	
ASSESSMENTS				
Pre-Operative QoR-15:	X			
Post-Operative QoR-15:				X
Vapour Consumption (ml):			X	
Time in Recovery (min):			X	
DATA ANALYSIS				X

3.2.8 Sample Size

Sample size calculation is based on estimation of the difference in mean post-operative Quality of Recovery (QoR) scores, after anaesthesia with desflurane or isoflurane. With a sample size of 85 in each group, a two-sided two-sample t-test at the 5% significance level, will have 80% power to detect a difference of 8 between the mean post-operative QoR scores with desflurane and isoflurane, assuming a standard deviation of 18.5. Sample size calculation was done on nQuery Advanced (Statistical Solutions Ltd, Cork, Ireland), Release 8.0.

A sample of 170, randomised in a 1:1 ratio to treatment with desflurane and isoflurane (85 per group) is proposed for this study.

3.2.9 Recruitment

Recruitment will be done by the Chief Investigator. The following steps will be followed:

1. Review the theatre booking list for theatre 11 the day before surgery.
2. Identify adult patients between the ages of 18 and 80 on the list, scheduled for general anaesthesia.
3. Review the patients in the ward:
 - a. Screen for any exclusion criteria.
4. Once confirmed that there are no exclusion criteria:
 - a. Explain the objectives of the study to the patient.
 - b. Hand the patient a patient information leaflet and discuss any questions the patient may have.
 - c. Take informed consent if the patient agrees to participate in the study.
5. Record the patient's name on a sequentially numbered list. This will be the only document to contain any personal information of the patient. It will be stored securely by the Chief Researcher. The number on the list will be the patient's study number and this number will be recorded on all study documents.

3.3 Assignment of Interventions

3.3.1 Allocation and Randomisation

Patients will be randomly allocated to either the control or the intervention group by computer randomisation. Randomisation and allocation will be managed remotely by the statistician, who will not be involved in patient care, and who will only gain access to study data after completion of data collection.

Block randomisation will be done to ensure that an equal number of patients are assigned to each treatment arm. Random block sizes will be used and the chief investigator, research assistant and treating anaesthetists will be blind to the size of each block.

Sequentially numbered, sealed, opaque envelopes will be prepared by the statistician. This will include a piece of paper indicating the group the patient has been randomised to. The sealed envelope will be handed to the treating anaesthetist on the day of surgery by the Chief Researcher. The Chief Researcher will be responsible for enrolment and assignment of participants.

3.3.2 Blinding

The patient will be blinded to the group they have been randomised to, as the vapour will only be started after induction of anaesthesia. The research assistant administering the post-operative QoR-15 will be blinded to the intervention.

The treating anaesthetist, the Chief Researcher and theatre staff will not be blinded to the intervention, as this would not be practical. All treating anaesthetists and theatre staff will be strongly inculcated not to disclose the allocation status of the participant at any time prior or after the general anaesthetic.

The piece of paper indicating the group will be attached to the Case Report Form. The Case Report Form will be collected by the Chief Researcher and will not be in the patient's file where it may unblind the patient or research assistant.

There are no circumstances under which unblinding will be permissible.

3.4 Data Collection

3.4.1 Source Documents

The following documents will be used as original source documents from which patient information will be gathered:

- Patient file: history, vital signs, comorbidities, previous anaesthesia and complications.
- Theatre booking list: patient age, type of anaesthesia.
- Blue anaesthetic report card: complete record of the anaesthesia care to the patient.
- Theatre record book: anaesthesia times, basic record of medications given.
- Nursing theatre record: anaesthesia times, recovery times, basic record of medications given.
- Stored history on the Datex-Ohmeda Aisys CS2 workstation in theatre 11: vapour consumption, anaesthesia times.

3.4.2 Study Documents

The following documents will be used as study documents to record relevant information:

- Case Report Forms (CRF)
 - CRF: Data Collection

- CRF: Pre-operative QoR-15 form
- CRF: Post-operative QoR-15 form
- Consent Form
- Patient Information Leaflet
- Standardised Anaesthesia Protocol

The templates for all the above documents are added to this protocol as Appendices.

3.4.3 Data Collection Procedures

Patients will be assessed by the chief researcher pre-operatively on the day before surgery. The demographic information on the Data Collection Form (Section A) will be completed. Information will be obtained from the patient's file, as well as from an interview with the patient. The chief researcher will accurately measure the patient's weight and height with the available scales and measuring devices in the wards.

Patients will then be asked to complete the QoR-15 in the language of their choice, as a measure of health status over the previous 24 hours. Where possible, the QoR-15 form will be handed to the patient to complete by themselves. However, in cases where patients are visually impaired, the items on the questionnaire will be read to them, and their responses recorded.

The following day, the treating anaesthetist will complete the information about the procedure in Section B of the Data Collection Form: anaesthetic time, amount of vapour used, additional medication administered, recovery time, any adverse events (bronchospasm, laryngospasm, post-operative nausea and vomiting and/or other), and whether the prescribed anaesthetic protocol was followed.

Post-operatively, a blinded observer (research assistant) will review the patient on the day following their surgery, prior to discharge. The patients will complete the QoR-15 again.

As follow-up will be done before discharge, retention of patients to follow-up should not present any difficulties.

3.5 Data Management

3.5.1 Database Entry

All study documents will be printed. All data will be recorded by hand on paper forms. After recruitment, the Chief Researcher will record the sequential study number on all documents relating to a particular patient.

The data will be captured electronically on the REDCap database by the research assistant (19). REDCap (Research Electronic Data Capture) is a secure, web-based application designed to support data capture for research studies, providing 1) an intuitive interface for validated data entry; 2) audit trails for tracking data

manipulation and export procedures; 3) automated export procedures for seamless data downloads to common statistical packages; and 4) procedures for importing data from external sources.

Data from each patient will be captured on REDCap sequentially so that the study number correlates with the database entry number.

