3.5.2 Data Storage

Study documents will be stored securely by the Chief Researcher. Documents will be kept in a dedicated lever-arch file and will be arranged sequentially according to study number. All study documents relating to a single patient will be stored together.

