1. If a small dose of muscle relaxant was used, ensure that it is fully reversed with Neostigmine 0.04mg/kg (2-3mg for most adults) 10-20 minutes before the end of the procedure. Glycopyrrolate or Atropine may be added to prevent bradycardia and gastro-intestinal side-effects.
2. At the end of the procedure, close the vapouriser and increase fresh gas flow to 6 l/min.
3. Remove the Laryngeal Mask Airway when clinically appropriate.

Managing Potential Problems:

1. Should the ophthalmologist complain that the patient is in too light a plane of anaesthesia, the patient may be deepened with a bolus of Propofol 0.5-1 mg/kg.
2. For intra-operative analgesia (for example if patient develops tachycardia or hypertension), administer 50-100 mcg Fentanyl boluses intravenously, as needed.
3. In cases where post-operative pain is anticipated, administer Tramadol 50-100mg intravenously as a bolus about 20 minutes before the end of the procedure.
4. For post-operative nausea (only if required), administer Ondansetron 4mg intravenously as a bolus, followed by Metoclopramide 10mg intravenously after 30 minutes (only if required).

Recording Data on the Case Report Form:

- Please ensure that you complete all the required fields on the Case Report Form.
- Please record any additional medication given to the patient as per above protocol to manage problems like post-operative pain or nausea.
- Please record adverse events on the Case Report Form and inform [name] immediately.
- In the unlikely event of Malignant Hyperthermia, please stop all volatiles and follow emergency management protocols.
- Please hand the Case Report Form to [name] at the end of the procedure, or place in the box in recovery room.
- The rest of the documents (consent form, quality of recovery forms) should remain in the patient's file.

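### The blinded assistant who takes the day-1 QoR-15 is also assigned database entry of the form that shows the treatment arm

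*Combined protocol and SAP*

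**What the plan says.** Two tasks are given to one role.

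- **Assessment.** Section 3.3.2: "The research assistant administering the post-operative QoR-15 will be blinded to the intervention". Section 3.4.3 confirms that the blinded observer on the day after surgery is the research assistant, and section 3.9 names this blinding as the control on observer bias.
- **Data entry.** Section 3.5.1: "The data will be captured electronically on the REDCap database by the research assistant". Section 1.4 pays the same role for both the visits and the entry. Section 4 has the paper records read in by study number, having just named the Data Collection Form and the QoR-15 forms as study documents.

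The Data Collection Form (section 6.7) has a Group field and the millilitres of vapour used. Section 3.3.2 adds: "The piece of paper indicating the group will be attached to the Case Report Form".

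The plan sees the risk and guards part of the path. The completed form "will be collected by the Chief Researcher and will not be in the patient's file where it may unblind the patient or research assistant" (section 3.3.2). Section 6.6 has the anaesthetist hand it over "or place in the box in recovery room", and says of the other papers: "The rest of the documents (consent form, quality of recovery forms) should remain in the patient's file". Section 3.5.2 puts custody with the Chief Researcher ("Study documents will be stored securely by the Chief Researcher") and combines the forms: "All study documents relating to a single patient will be stored together".

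**The concern.** To enter the Data Collection Form, the assistant has to read the arm. The safeguard in section 3.3.2 keeps that form out of the patient's file. Nothing equivalent applies when the assistant later receives it for entry.

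The main exposure is to later patients. An assistant who has entered earlier forms knows those allocations, and in 1:1 blocks they partly predict the next one. Concealing the block sizes (section 3.3.1) reduces this but does not remove it once the past sequence is known. The assistant has some room to influence the primary endpoint: reading items aloud and recording answers for visually impaired patients (section 3.2.4), and asking patients to complete omitted items at the bedside (section 3.5.3).

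The trial is described as observer blinded. If the assessor has seen allocations while still assessing patients, that description cannot be defended in the report, and no analysis can restore it.

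**Working it through.** **1. Follow the form.**

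| Stage | Who holds the Data Collection Form | Rule keeping the assistant from it |
|---|---|---|
| Theatre and recovery | Anaesthetist, then Chief Researcher or recovery-room box (3.3.2, 6.6) | Kept out of the patient's file |
| Storage | Chief Researcher, in one file with the QoR-15 forms (3.5.2) | Custody only |
| REDCap entry | Research assistant (1.4, 3.5.1) | None found |

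**2. Is timing fixed anywhere?** No. Sections 3.5.1 and 4 fix the order of entry (by study number), not its date. The opening reference in 3.5.1 to the period after recruitment concerns numbering each patient's documents, not entry. Two passages lean towards entry during the trial. Section 1.4 budgets visits and entry together as 2 h × 25 days × 6 months = 300 h, which at R100 reproduces the stated R30 000. Section 3.7.1 has the database entries checked periodically. Neither is proof. Nothing shows a form being entered before that patient's own visit.

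**3. How predictable would later allocations be?** This is illustrative, and applies only if entry runs during recruitment.

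- From the plan: 170 patients, 1:1, random block sizes (3.2.8, 3.3.1).
- Assumed: the block sizes, each equally likely, because the plan rightly conceals them; and an assistant who guesses the arm with fewer known allocations (ties count 0.5).
- *L* is the number of most recent allocations not yet known.

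Proportion guessed correctly, *p*, from 6,000 simulated sequences per row:

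| Block sizes | L=0 | L=1 | L=2 | L=3 | L=5 |
|---|---|---|---|---|---|
| 4, 6 | 0.692 | 0.593 | 0.556 | 0.520 | 0.500 |
| 4, 6, 8 | 0.680 | 0.596 | 0.565 | 0.533 | 0.508 |
| 2, 4, 6 | 0.702 | 0.577 | 0.547 | 0.516 | 0.500 |
| 2, 4 | 0.722 | 0.555 | 0.527 | 0.500 | 0.500 |

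Hand check of the last row:

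- *L* = 0. A block of 2 gives 1/2 + 1 = 1.5 expected correct guesses. A block of 4 gives 1/2 + 2/3 + 2/3 + 1 = 2.833. The mean block length is 3, so *p* = [(1.5 + 2.833)/2]/3 = 0.722.
- *L* = 1. A block of 2 gives 1/2 + 1/2 = 1. A block of 4 gives 1/2 + 1/2 + 2/3 + 2/3 = 2.333. So *p* = [(1 + 2.333)/2]/3 = 0.556, against 0.555 simulated.

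**4. What would reach the treatment comparison?** Suppose a score is *d* points higher when the assistant believes the patient is in one arm rather than the other. The expected between-group difference is *dp* − *d*(1 − *p*) = *d*(2*p* − 1). The multiplier 2*p* − 1 is:

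- *L* = 0: 0.36 to 0.44
- *L* = 1: 0.11 to 0.19
- *L* = 3: 0.00 to 0.07

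The documents give no basis for *d*, so this stops at the multiplier.

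**5. Which lag is realistic?** Section 3.2.1 reports 166 general anaesthetics in 6 months. On the budget's calendar that is 166/(25 × 6) = 1.1 a day, before eligibility and consent. Prompt entry after each visit could therefore leave a lag of zero or one patient; batched entry would lengthen it. The documents do not settle this.

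**The case against.** The best defence is that harm needs a fact the plan does not state. If all entry follows the last day-1 visit, no assessment is affected. Section 3.3.2 also closes by ruling out unblinding in any circumstances, and the Chief Researcher, who holds the papers, could enforce that. On this view only an operating instruction is missing. The patient is blinded, rates the score and completes the form alone where possible, so the assistant's influence is limited. The guessing figures also stack several assumptions, and they fall quickly once a few allocations are unknown.

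Most of this is fair on size. Timing is not shown, the effect is probably modest, and the no-lag figures should not be read as expected values. It does not remove the gap. A general prohibition supplies no mechanism, and here it stands beside a task that would breach it whenever the Data Collection Form is entered while visits continue. Custody does not help either, since the plan assigns the papers to the assistant for entry.

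One point cuts the other way. The plan protects a form, not every route to the allocation. Section 3.4.1 lists the anaesthetic report card as a full record of the anaesthetic, and where it is kept on day 1 is not stated.

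**Conclusion.** The concern holds. The plan makes one person both the blinded assessor of the primary endpoint and the entry clerk for a form that names the arm, and nothing on timing, access or person reconciles the two. Confidence is high that the gap exists; that it would operate is plausible but not shown.

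If entry runs alongside recruitment, and under the assumed block sizes and guessing rule, later allocations could be guessed in about 55-60% of patients at a lag of one and 50-53% at a lag of three, with 68-72% when nothing is missing. These are illustrations, not bounds. Exposure is greatest where items are read aloud, and the documents do not say how many patients that covers. The gap should be closed because the remedy is cheap and the affected control is one the plan relies on; it is not a reason to doubt the design as a whole.

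**What to change.** **Section 3.5.1.** State that, until the last day-1 QoR-15 has been completed, the assistant enters only the QoR-15 forms, under the same study number, with REDCap rights that hide the Data Collection Form and the group. Preferably, hold entry of the Data Collection Form and slip until that point. Alternatively, the Chief Researcher, who is already unblinded, enters that form.

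**Section 3.5.2.** State that the assistant has no access to the combined patient file until then. Section 6.6 leaves the QoR-15 forms in the patient's file, so separate filing is needed only if the assistant would otherwise take them from the combined file.

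**Cost.** Two wording changes and one database setting, with no extra staff. At an assumed 5 to 15 minutes a form, 170 forms take 170 × 5/60 = 14.2 h to 170 × 15/60 = 42.5 h.

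- *If entry is held:* at the budgeted 2 h a day this is 7 to 21 working days after the last visit, in or close to August 2021, the month section 1.5 gives to analysis. Database checks of that form under section 3.7.1 come late, though checks on paper can continue.
- *If the Chief Researcher enters it:* the same hours move to that person, who would then be checking their own entries.
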